3.7.1.2. Follow-up visits

The follow-up visits consist of the entry of data resulting from the following Standard of Care examinations and procedures obtained from the patients' regular follow-up visits:

1. Confirm that the participant wishes to continue in the study
2. Review and documentation of changes in medical and ophthalmic history
3. Documentation of vitamin A supplement use
4. Refraction and best-corrected visual acuity (BCVA) using the Early Treatment Diabetic Retinopathy Study (ETDRS) Testing Protocol [32]
5. Microperimetry
6. Ophthalmic examination
7. Spectral-domain optical coherence tomography
8. Fundus autofluorescence

The data from the visits will be utilized in the study even if the order of the examinations change from visit to visit or between the practices of the different investigators, and the examinations are performed on different days (as long as the time window is respected).

3.7.2. Safety Assessments

Due to the observational design of the natural course study, no study specific safety assessments are needed.

3.7.2.1. Adverse Events

Due to the observational design of the natural course study, no adverse events are expected.

3.7.2.2. Clinical Laboratory Data

Not applicable

3.7.2.3. Evaluations

During each participant's visit to the clinic, a clinician participating in the study will record "study progress notes" to document all significant observations. At a minimum, this documentation will contain:

- The informed consent process, including any revised consents
- The date of the visit and the corresponding Visit, Day, or Week in the study schedule
- The genetic information at baseline
- Any comments made by the participant about the study, including any significant medical findings
- Any changes in Vitamin A supplement use
- A general reference to the procedures completed
- The signature (or initials) and date of all clinicians who made an entry in the progress notes
- The evaluation of refraction and best corrected visual acuity according to ETDRS
- The evaluation of full-field electroretinogram in at least one eye at baseline (or within the past five years)
- The evaluation of microperimetry test and recording of mean sensitivity

- The evaluation of spectral-domain optical coherence tomography (sd-OCT)
- The evaluation of fundus autofluorescence
- A summary of the ophthalmologic exam including status of the anterior segment of the eyes, including the cornea, anterior chamber, iris and grading cataract, and dilated fundus exam

In addition, any contact with the participant via telephone or other means that provides significant clinical information will also be documented in the progress notes as described above. Information from the study progress notes and other source documents will be promptly transcribed to eCRFs for transmission to the Coordinating Center. Any changes to information in the study progress notes, other source documents, and CRFs will be properly tracked.

3.7.2.4. Labs Performing Evaluations and Special Precautions

Not applicable

3.7.2.5. Sharing Research Results

As the data collected during study participation in this observational study is collected from standard clinical care ophthalmologist visits, the results of each individual's procedures conducted during the time period of patients' participation in this study, including any clinically significant abnormal findings, will be shared with that study participant or his/her primary care provider throughout the study.

3.7.3. Endpoints

3.7.3.1. Primary Statistical Endpoint

The primary endpoint is the rate of growth of atrophic lesions as measured by FAF imaging, calculated at 12 and 24 months.

3.7.3.2. Secondary Statistical Endpoints

The secondary endpoints are:

- Rate of retinal thinning and photoreceptor loss as measured by sd-OCT calculated at 12 and 24 months.
- Loss of retinal sensitivity as measured by microperimetry calculated at 12 and 24 months.
- Change of best-corrected visual acuity by using the ETDRS protocol calculated at 12 and 24 months.

3.7.4. End of Study

The End-of-Study date for each participant is defined as the last date of contact with the participant, or the last date an attempt was made to contact the participant, recorded on the follow-up CRF page. Typically, the End-of-Study date will be the date of the 24 month follow up visit.

3.8. Withdrawal Criteria, and Procedures

All participants have the right to withdraw from the study at any time, for any reason, without prejudice. The investigator may discontinue any participant's participation when in the investigator's judgment it is necessary for any reason. This can include the failure of a participant to comply with the protocol or when the investigator considers withdrawal is in the best interest of the participant.

When a participant is withdrawn from participation in the study, or if the study is terminated prematurely, the investigator will collect all data from previous study visits at the last scheduled visit, or will request that the participant return for a follow-up visit. All measurements will be recorded in the source documents and on the electronic clinical report form.

When a participant decides to withdraw study consent, an investigator at the site will attempt to contact the participant and determine the reason that led the participant to the decision. When known, the reasons for withdrawal shall be fully evaluated and recorded appropriately in source documents and the eCRF.

If the study sponsor, the Foundation Fighting Blindness Clinical Research Institute (FFB CRI), discontinues the study for any reason, such reasons will be thoroughly documented in the source documents and eCRFs, and all local study site IRB's and HRPO will be notified immediately.

3.9. Screen Failures

A screen failure participant candidate is a study candidate who has provided written informed consent for participation but who is not entered into the study.

3.10. Definition of Completed

The study period is defined as the time period during which participants are evaluated for the primary and secondary objectives of the study. Participants who complete all follow-up studies and are evaluated at the last scheduled visit of their study period will be defined as having completed the study.

3.11. Definition of Lost to Follow-up

Study participants who miss a follow-up study visit and cannot be contacted after multiple contacts at different times of day during a period of 10 days, and who do not have a known reason for discontinuation (e.g., withdrew consent) will be classified as “lost to follow-up”.

3.12. Participant Compliance

Not applicable.

3.13. Protocol Deviations

This study shall be conducted according to this written protocol except in the case of an emergency where immediate intervention based on the judgment of the investigator (or a responsible, appropriately trained professional designated by the investigator) is essential for the protection, safety, and well-being of the participant. In the event of a significant deviation from the protocol as a result of an emergency, accident, or mistake, the investigator or designee must contact the Study Director, as soon as possible, by telephone. A joint decision will then be made regarding the participant’s continuation in the study and the decision documented by the investigator and the Study Director and reviewed by the monitor. In addition, the investigator must notify the IRB to the extent necessary under GCP and local requirements. The sponsor, the Foundation Fighting Blindness Clinical Research Institute shall be notified of any protocol deviations and shall forward a detailed report any serious deviations to HRPO immediately. Any non-serious deviations shall be reported to HRPO as part of the annual study progress report.

3.14. Protocol Modifications

No changes shall be made to this protocol by site principal investigators or any other site staff without prior written consent and approval from the Study Director, the Sponsor [the Foundation Fighting Blindness Clinical Research Institute (FFB CRI)], their respective IRBs, and HRPO. Amendments shall be submitted to the IRBs for review and approval prior to implementation. Any permanent change to the protocol, whether an overall change or a study center specific change(s), must be treated as a protocol amendment. Any amendment to the protocol that is deemed necessary as the study progresses will be fully discussed by the investigator(s). Except for administrative amendments, investigators must await IRB approval of protocol amendments before implementing the change(s). Administrative amendments are defined as amendments that do not affect the safety of the research participants, the scope of the investigation, or the quality of the trial. However, if a protocol amendment is required to eliminate an apparent and immediate hazard to participants, the amendment should be implemented immediately, and the IRB notified within 5 days.

Any deviation to the protocol that may have an effect on the safety or rights of the participant or the integrity of the study must be reported to the local IRBs and to the USAMRMC ORP

HRPO as soon as the deviation is identified. Any corrective actions taken to avoid future deviations shall be included in the report.

All unanticipated problems involving risk to participants or others related to participation in the study should be promptly reported by [contact]), by email ([contact]), or by [contact]) to the USAMRMC, Office of Research Protections, Human Research Protection Office. A complete written report will follow the initial notification. In addition to the methods above, the complete report will be sent to the U.S. Army Medical Research and Materiel Command, ATTN: MCMR-ZB-PH, [name].

When, in the judgment of the chair of the local IRB and the investigators, the amendment to the protocol substantially alters the study design and/or increases the potential risk to the participant, the current approved written informed consent form shall be revised and if applicable, the participants shall be asked to sign a new written informed consent.

Major modifications to the research protocol and any modifications that could potentially increase risk to participants will be submitted by the Sponsor to the USAMRMC ORP HRPO for approval prior to implementation. All other amendments will be submitted by the Sponsor with the continuing review report to the USAMRMC ORP HRPO for acceptance.

4. Study Personnel

4.2. Conflict of Interest

As this protocol does not support the development of a drug, device, or other intellectual property, there is no immediate concern about conflict of interest. If any concerns arise, conflict of interest statements will be obtained on a case-by-case basis.

5. Prohibited Medications

Study participants may use any systemic medications that are necessary. However, study participants shall not participate in, or take concomitant therapy, to treat Stargardt disease. Study candidates who have previously participated in an interventional study for Stargardt disease are also excluded – see study exclusion criteria.

6. Evaluation of Adverse Events

Not applicable.

7. Statistical Analysis

7.1. Sample Size and Power

[figure not shown]
Prior to establishing this study protocol, a feasibility survey was undertaken. The survey consisted of a questionnaire that was sent to the participating centers to determine how many study candidates might be available at each center for this prospective study.

The primary outcome of the study is **the yearly growth in the area of the atrophic lesion** as measured by fundus auto-fluorescence. A recent paper by Chen et al [34] reported that in a group of 24 STGD participants with well defined atrophic lesions at baseline, the mean yearly growth of the lesion was $0.94 \text{ mm}^2 \pm 0.87$.

The reliability of measuring areas of geographic atrophy using images taken with a confocal scanning laser ophthalmoscopy has been described by Deckert et al [35]. Using 2 different readers to examine images from 34 eyes, the mean difference in area affected for the proposed quantification algorithm was 0.12 mm^2 with a 95% confidence interval (0.02, 0.22).

Using the above parameters as a reference, we calculated the power to detect yearly progression for sample sizes between 120 and 240 participants, with standard deviations between 0.9 and 1.1, and expected progression rates of 0.40 and 0.50 mm² per year (Figure 5). A clinically meaningful progression rate should be greater than the variability of the measurement. The power calculations were set to test for progression rates above 0.2 mm² which is the estimate of the upper bound of the difference that could be attributable solely to measurement error.

Power to detect progression rates for a range of sample sizes and standard deviations with a two-sided significance level $\alpha=0.05$ *

*Assuming that test retest differences could be as high as 0.2

Figure 5: Power calculations for expected progressions rates of 0.40 and 0.50 mm² per year

A sample size of 170 achieves 80% power to detect a difference of 0.2 between the null hypothesis mean of 0.2 mm² (measurement error) and the alternative hypothesis mean progression of the lesion of 0.4 mm² with an estimated standard deviation of 0.9 and a significance level $\alpha= 0.05$ using a two-sided Wilcoxon test (Figure 5 (a)). Similarly, if the expected standard deviation increases to 1.0 we need 200 participants to achieve the same level of power. When the expected progression rate is ≥ 0.50 mm², a sample size of 120 participants achieves more than 80% to detect differences beyond the expected measurement error, for standard deviations ≤ 1.1 (Figure 5 (b)).

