1.1 Background

Any new therapeutic clinical studies must be able to compare the intervention to the natural history of the disease in a longitudinal study. Therefore, the natural history of the disease in the patients to be treated must be understood. Any clinical outcome measures must be accurate, reproducible and have acceptably small intra- and inter-observer variability. For surrogate measures, the FDA states that “validated surrogate markers are those for which evidence has been established that a drug-induced effect on the surrogate predicts the desired effect on the clinical outcome of interest” [13].

Degeneration of the photoreceptors and underlying retinal pigment epithelium (RPE) in STGD, as measured by standard histology and sd-OCT imaging, typically occurs close to and within the macula [14] (Figure 2). Multiple lines of evidence indicate that lipofuscin accumulation in the RPE is responsible for RPE cell death [15-17], most probably by facilitating apoptosis and damage to lysosomal membranes [15]. Following RPE loss, photoreceptor cells degenerate rapidly [18] because of their dependence on RPE cells for the maintenance and the removal of shed photoreceptor outer segments.

Figure 2:

[figure not shown]

Figure 2: (A) A Fundus Autofluorescence (FAF) image of a Stargardt patient’s retina. The diameter of the central area of “absent FAF” corresponds to geographic atrophy seen clinically with a larger diameter of “abnormal FAF” visible. (B) An sd-OCT image through the fovea of a normal control eye. (C) An sd-OCT image showing the extent of the transverse loss of the inner segment-outer segment junction of the photoreceptors in the foveal region. (D) A comparison of the measurements obtained from FAF in (A) and sd-OCT in (C). [14]

During the part of the visual cycle that occurs in the discs of the outer segment of photoreceptors, opsin bound 11-cis-retinal is converted by light into all-trans retinal. This conformational change triggers a signaling cascade and is followed by the release of all-trans-

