2.1 Study Rationale

Although STGD is the most prevalent form of juvenile-onset macular dystrophy, with an estimated incidence of 10 – 12.5 per 100,000, it is still relatively rare and there is very limited information available about the natural course of the disease in larger numbers of STGD patients. The information currently available is predominantly based on individual reports of patient data collected from single centers [28, 29]. However, this limited data clearly points to a disease which is very heterogeneous with significant variation in the age of onset and rate of progression, and limited clear correlations between phenotype and genotype [30, 31]. These limitations highlight the urgent need for a multi-center study that documents the natural course of the disease. The information gathered from this proposed study should provide guidance and support to the identification of the most appropriate clinical outcome measures for anticipated clinical trials. It may also be used to identify and support the validation of surrogate clinical trial endpoints that are offered by recent technological advances in retinal imaging capabilities, such as fundus autofluorescence (FAF) and spectral-domain optical coherence tomography (sd-OCT).

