7.2. Statistical Analyses

Estimating **the yearly growth in the area of the atrophic lesion** as measured by fundus auto-fluorescence:

First exploratory analysis looking at the baseline, six, and twelve months overall distribution of the outcome will be performed, outliers and inconsistent measures will be identified and reviewed. Let Y_{iv} represent the area (or a transformation to achieve normality; e.g. square

root) of the i^{th} individual at visit v for $v=0, 1, 2, 3, 4$ for the baseline, 6 months, 12 months, 18 months and 24 months visits, respectively. In order to determine the average rate of progression in the population, an appropriate approach will be to allow for each individual to have his/her own intercept and slope and to average them to achieve the overall rate of decline. This is accomplished with a random coefficients regression model of the form:

$$Y_{iv} = (\mu + a_i) + (\Delta + b_i)v + \gamma Z_{iv} + e_{iv}; \text{ where } a_i \sim N(0, \sigma_1^2), b_i \sim N(0, \sigma_2^2), \text{ cov}(a_i, b_i) = \sigma_{12} \text{ and } e_{iv} \sim N(0, \sigma^2).$$

The a_i and b_i are the random departures of the line for the i^{th} individual from the population line with intercept μ and slope Δ . The e_{iv} are the within individual departures from the line of the repeated measurements taken on the i^{th} individual at times 0, 6, 12, 18 and 24 months. Z_{iv} represents a vector of factors that could to be related to progression such as age and use of vitamin A supplementation.

The estimate of Δ and its standard error will provide the six month progression of the lesions. In addition, to explore whether progression may be different for different initial levels, we will carry out the analysis in strata of baseline severity.

A similar approach to will be used to examine progression overtime for the secondary outcomes: retinal thinning, loss of photoreceptors, loss of retinal sensitivity, and changes of BCVA.

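### Does it matter that the 0.2 mm² per year null in the power calculation is called a bound on measurement error, when its source is a confidence interval for a mean?

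*Protocol*

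**What the plan says.** PROGSTAR-02 section 7.1 takes its measurement-error figure from one cited reliability study: "Using 2 different readers to examine images from 34 eyes, the mean difference in area affected for the proposed quantification algorithm was" (the sentence goes on to give a value of 0.12 mm², 95% CI 0.02 to 0.22). It then gives a criterion, "A clinically meaningful progression rate should be greater than the variability of the measurement", and sets the null growth rate at 0.2 mm² per year, described as "which is the estimate of the upper bound of the difference that could be attributable solely to measurement error". The note to the power figure adds: "Assuming that test retest differences could be as high as 0.2".

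The power statement reads "A sample size of 170 achieves 80% power to detect a difference of 0.2 between the null hypothesis mean"; the null is 0.2 and the alternative 0.4 mm², with SD 0.9 and a two-sided Wilcoxon test at 5%. PROGSTAR-01 section 7.1 repeats all of this, and the SMART form (section 7c) copies the main text.

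The planned analyses estimate slopes. In PROGSTAR-02 section 7.2, the slope of a random coefficients model and its standard error "will provide the six month progression of the lesions". PROGSTAR-01 section 7.2 fits a line per individual and regresses the slopes on risk factors. The SAP estimates a yearly rate with a linear mixed model. None names a Wilcoxon test or a comparison with 0.2.

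**The concern.** Three things look wrong.

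- **The label.** A confidence interval for a mean limits the average difference between readers. It does not limit how far two readings of one eye can differ, and a two-reader comparison is not a test-retest study. The protocol uses the same 0.2 for all of these.
- **The scale.** A difference in area at one time (mm²) becomes a yearly rate (mm² per year) with no stated assumption.
- **The link to the analysis.** The 80% belongs to a test that the analysis sections do not contain, so the plan gives no rule for deciding that growth exceeds measurement error.

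The stake would be a misleading picture of reader variability. PROGSTAR-02 section 1.1 wants outcome measures to "have acceptably small intra- and inter-observer variability", and section 2.1 says the study should support the "identification of the most appropriate clinical outcome measures for anticipated clinical trials". If 0.2 also fed wrongly into the sample size, the study could be underpowered.

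**Working it through.** **1. The plan's own figure.** Inputs from section 7.1: null 0.2, alternative 0.4, SD 0.9, two-sided 5%, power 80%.

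- Normal approximation: n = (0.9 × (1.960 + 0.842) / 0.2)² = 158.9. With the t distribution, n = 161.
- Wilcoxon signed-rank under normality (efficiency 3/π): 161 × π/3 = 168.6, so 169, against 170 stated.
- Power at 170 is 80.4%, or 80.8% by simulation of the signed-rank test.
- The companion statements give 78.5% (SD 1.0, n = 200, stated as 80%) and 82.5% (rate 0.5, SD 1.1, n = 120, stated as more than 80%).

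**2. What the interval says about single differences.** The half-width is 0.10 with 34 eyes, and t(0.975, 33) = 2.0345.

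- Implied SD = 0.10 × √34 / 2.0345 = 0.287.
- If all 34 differences lay within ±0.2 with mean 0.12, the largest possible SD is √((0.2 − 0.12)(0.12 + 0.2) × 34/33) = 0.162. The half-width could then be at most 2.0345 × 0.162 / √34 = 0.057, well short of 0.10.
- The smallest symmetric bound compatible with the interval is √(0.287² × 33/34 + 0.12²) = 0.31 mm².
- If the differences are signed and normal (an assumption), 95% of them lie in 0.12 ± 1.96 × 0.287, that is −0.44 to 0.68.

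So 0.2 does not bound single differences. Rounding of the published limits does not rescue it, nor does treating the eyes as 17 independent units: the largest half-width then is 0.087, while rounding allows no less than 0.095.

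**3. Whether this reaches the power calculation.** The null is a mean. Random reading error averages out of a mean and acts through the SD; only a systematic difference shifts the mean. The relevant limit is therefore that of the mean reader difference, 0.22, or about 0.2. The cited prior growth, 0.94 ± 0.87, is measured growth, so its SD should already contain reading error. Adding 0.287 again in full gives √(0.87² + 0.287²) = √0.839 = 0.92, inside the planned 0.9 to 1.1.

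**4. The yearly scale.** Suppose a systematic offset of 0.2 mm² lies between two readings (an assumption).

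| Pattern of the offset | Effect on the yearly rate |
|---|---|
| Readings 12 months apart | 0.20 |
| Readings 24 months apart | 0.10 |
| Readings 60 months apart | 0.04 |
| Same at every visit | 0 |
| Five-visit slope, last visit only | 0.2 × 1 / 2.5 = 0.08 |
| Five-visit slope, last two visits | 0.2 × 1.5 / 2.5 = 0.12 |

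The five-visit rows use times 0, 0.5, 1, 1.5 and 2 years, with a sum of squared deviations of 2.5. Among these patterns, 0.2 per year is the most demanding null. With a null of 0.10, power at n = 170 is 98.8%.

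**5. The comparison the analysis allows.** With a six-month slope Δ, the yearly rate is 2Δ and its approximate lower 95% limit is 2Δ − 1.96 × 2 × SE(Δ). Setting that limit against 0.2 needs nothing beyond the planned output. Taking one rate per participant, SD 0.9 and true rate 0.4, the chance that the limit exceeds 0.2 is 77% at n = 150, 82% at 170 and 94% at 250.

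**6. Sensitivity of the Wilcoxon figure.** Power is 75% at the minimum enrolment of 150, and 72% at n = 170 if the null is the unrounded 0.22. The rate detectable with 80% power then moves from 0.40 to 0.42. At the cited growth of 0.94, power is near 100%.

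**The case for a change.** The case for amending is that the wording is wrong on the protocol's own figures. Someone planning a later trial could take 0.2 mm² as the most two readings will differ, when under normality about half of single differences would exceed it. The criterion in section 7.1 speaks of measurement variability, and no analysis section says how it will be applied. Power at the permitted minimum of 150 is 75%, which section 7.1 does not show. The repair would be a few words and one SAP line, with no extra patients or visits.

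The wording point stands: the figure note and the variability sentence describe a limit on a mean as if it limited individual differences. The rest carries less weight. Later trials are to be guided by the data this study collects, not by a planning constant. The power statement is correct for the conditions it names and does not claim 80% at 150. The study's objective is to estimate a rate, with no confirmatory decision attached, and sizing a slope study by a one-sample test is a common approximation. A fixed rule against 0.2 would also commit the SAP to a threshold that could fairly be 0.20, 0.10 or zero, and to the untransformed scale, although section 7.2 leaves a square-root transformation open.

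**Conclusion.** No change to the plan follows. The label is loose: 0.2 mm² is an approximate upper limit for the mean difference between two readers, while the implied SD of single differences is about 0.29 mm². As a null for mean yearly growth, 0.2 is defensible and mostly conservative, and 170 participants give the stated 80% (80.4% recomputed). The missing comparison is a gap that any analyst fills from the slope and its standard error, with about the same power (82% against 80% at 170). Correcting the words would move neither the sample size, the null nor any estimate.

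This rests on a few assumptions. Yearly rates are taken as roughly normal, with one rate per participant, although both eyes may be included. The published interval is taken to be a confidence interval for the mean, as the protocol says. Were it limits of agreement instead, the SD would be 0.10 / 1.96 = 0.05 and 0.2 would be a fair bound even for single differences. That 0.2 derives from the 0.22 limit is an inference, since section 7.1 gives no other source. None of these numbers bears on the scotopic sensitivity outcome of SMART.

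### PROGSTAR power section: the null rate is described as the upper bound of measurement error, which the quoted data put at 0.22 mm², but power is computed at 0.2; at 0.22, 170 participants give about 72%, not 80%

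*Protocol*

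**What the plan says.** PROGSTAR-02, section 7.1, quotes one reliability result for measuring atrophic area: two readers, 34 eyes, mean difference 0.12 mm² "with a 95% confidence interval (0.02, 0.22" mm²). It takes the quoted parameters as its reference and sets the calculation up to test for rates above 0.2 mm², "which is the estimate of the upper bound of the difference that could be attributable solely to measurement error". The footnote to the power figure likewise allows test–retest differences of up to 0.2.

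The sample size statement follows: "A sample size of 170 achieves 80% power to detect a difference of 0.2 between the null hypothesis mean of 0.2 mm²" and "the alternative hypothesis mean progression of the lesion of 0.4 mm² with an estimated standard deviation of 0.9", "using a two-sided Wilcoxon test" at alpha 0.05. The section adds that 200 participants are needed if the SD is 1.0. For a rate of 0.50 mm² or more, it says that "a sample size of 120 participants achieves more than 80% to detect differences beyond the expected measurement error" for SDs up to 1.1.

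PROGSTAR-01, section 7.1, carries the same text and numbers, and the SMART protocol copies them into its section 7.c. The synopses of PROGSTAR-01 and PROGSTAR-02 give an enrolment of 150 to 250.

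**The concern.** The null is justified as the most that measurement error alone could produce. Among the quoted data, the figure with that role is the upper confidence limit, 0.22. A bound that is rounded down no longer bounds.

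The second decimal matters because the difference to be detected is itself small. Against an alternative of 0.40, it is 0.20 with a null of 0.2 and 0.18 with a null of 0.22. Required sample size varies with the inverse square of that difference, so it rises by a factor of (0.20/0.18)² = 1.23. At stake are the stated 80% for 170 participants, the companion figure of 200, and the claim that 120 are enough for SDs up to 1.1.

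**Working it through.** **Inputs, all from section 7.1.** Alternatives 0.40 and 0.50 mm² per year; SD 0.9, 1.0 and 1.1; two-sided alpha 0.05; Wilcoxon test; null 0.2 as declared, or 0.22 as the quoted upper limit.

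**Assumptions.** One-sample signed-rank test of a single cohort against the null rate, with normal data, so that the Wilcoxon efficiency relative to the t test is 3/π = 0.955. No allowance for dropout; the section gives none.

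**Formulas**, with d = alternative − null:

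- Power = Φ[(d/SD)·√(N·3/π) − 1.960]
- N for 80% = [(1.960 + 0.842)·SD/d]² ÷ (3/π)

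Each power was also obtained from a noncentral t distribution with N·3/π in place of N. The three printed cases were simulated at both nulls (40,000 signed-rank replicates each).

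**Step 1: the plan's own figure.** N = 170, SD 0.9, d = 0.20. √(170 × 0.955) = 12.74, and 12.74 × 0.20/0.9 = 2.831. Then 2.831 − 1.960 = 0.871, so power is 80.8% (noncentral t 80.4%, simulation 80.7%). N for 80% is 167. The printed 170 and 80% therefore reproduce at a null of 0.2.

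**Step 2: the same case at 0.22.** d = 0.18. 12.74 × 0.18/0.9 = 2.548, and 2.548 − 1.960 = 0.588, so power is 72.2% (noncentral t 71.7%, simulation 71.9%). A plain z test gives 74.1% and a plain t test 73.7%. N for 80% is 206 (208 by noncentral t), about 39 more than the 167 of step 1 by the same formula.

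**Step 3: all three printed cases** (normal approximation / noncentral t, Wilcoxon)

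| Case | Printed | Null 0.2 | Null 0.22 | N for 80% at 0.22 |
|---|---|---|---|---|
| N = 170, rate 0.40, SD 0.9 | 80% | 80.8 / 80.4% | 72.2 / 71.7% | 206–208 |
| N = 200, rate 0.40, SD 1.0 | 80% | 78.9 / 78.5% | 70.1 / 69.7% | 254–256 |
| N = 120, rate 0.50, SD 1.1 | above 80% | 83.1 / 82.5% | 77.8 / 77.1% | 127–129 |

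In the third case even a plain z test reaches only 79.6% at 0.22. At SD 1.0 the same 120 participants give 85.0 / 84.4%, so that part of the claim survives.

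**Step 4: could another variant explain 80% at 0.22?** No two-sided variant does for N = 170. A one-sided Wilcoxon test would give 81.7%, but the plan states a two-sided test and its figure already reproduces with one at a null of 0.2.

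**Step 5: planned enrolment, rate 0.40, null 0.22.** At SD 0.9, 150 participants give 66–67% and 250 give 87%. At 250, power is 79% for SD 1.0 and 71–72% for SD 1.1.

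**The case against.** A reader might infer an arithmetic error. The documents do not support that. Section 7.1 itself names 0.2 as its estimate of the bound, the figure footnote repeats it, the null used agrees, and 80% follows. What remains is an unexplained gap between that estimate and the limit quoted just before it.

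A second objection is that the cited values are only a reference and that other inputs lean the other way. The cited growth SD of 0.87 becomes 0.9 to 1.1, and the cited mean growth of 0.94 mm² per year becomes 0.40 or 0.50. This is fair and limits the weight of the point. It does not restore the printed figure: with null 0.22 and SD 0.87 both unrounded, 170 participants give 12.74 × 0.18/0.87 − 1.960 = 0.676, or 75%.

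Third, 0.22 is itself a proxy. It is the confidence limit of a mean inter-reader difference, from a study of geographic atrophy in age-related macular degeneration, and not a bound on error in yearly growth. That is true. The point takes the plan's choice of bound as given and asks only that the number used match it or be explained.

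Fourth, a reader might infer that the studies are underpowered or that the enrolment cap is too low. The documents do not support this either. Section 7.1 presents 170 as one scenario, not as the enrolment target. At SD 1.0 the need for about 255 against a cap of 250 amounts to 79% rather than 80% power. The figure of 120 lies below the enrolment minimum. PROGSTAR-02 section 7.2, PROGSTAR-01 section 7.2 and the SAP all estimate slopes, and none describes a test against 0.2 or 0.22.

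**Conclusion.** The point holds as a mismatch between the null rate and its stated source. The rounding is unexplained and favourable to the plan. At 0.22 it costs 8 to 9 percentage points of power in the 170 and 200 cases and about 5 points in the 120 case, where the claim of more than 80% fails at SD 1.1 only.

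These figures rest on normal data, a one-sample signed-rank test, efficiency 3/π and no dropout. With a z or t test the 170 case rises only to about 74%.

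The effect is confined to the stated power. The cited mean growth of 0.94 mm² per year is far above either null, and no planned conclusion depends on this threshold. The copy in SMART concerns lesion area, so correcting it says nothing about power for SMART's own outcome, scotopic macular sensitivity.

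**What to change.** In section 7.1 of PROGSTAR-02 and PROGSTAR-01, do one of the following:

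- Carry 0.22 into the calculation, restate the three cases as in the table above, redraw the power figure, and give power across the enrolment range of 150 to 250 (step 5).
- Keep 0.2, state why it is preferred to the quoted limit of 0.22, and show the 0.22 results beside it.

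If the SMART copy is kept, align it and say that it refers to lesion area.

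The cost is one rerun of the calculation, an edited paragraph and a less favourable stated power. Enrolment, visits and analysis stay as they are.
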